- ^d Hospitalization for TLS monitoring and prophylaxis: All subjects will be hospitalized to monitor for TLS. Hospitalization will begin within 24 hours before the first dose of AMG 176 and continue until 24 hours post first AMG 176 dose. If the target dose is 180 mg/m² or higher, hospitalization will also be required within 24 hours before administration of the target dose on day 8 and will continue until 24 hours post administration. Hospitalization period can be increased per institutional standards or investigators discretion. Hospitalization for the purpose of TLS prophylaxis will not be captured as an SAE.
- e TLS Prophylaxis: See Protocol for prophylaxis requirements (see Section 11.9) including additional serum chemistry and hematology laboratory samples that must be collected within 24 hours prior to the first dose (see Section 8.4.3.2). Electrolyte values must be within normal range prior to AMG 176 dosing.
- f AMG 176 dosing: AMG 176 will be administered QW IV on days 1, 8, 15, and 22 on a 28-day cycle. A lead in dose of 120 mg/m² will be required if the target dose is 180 mg/m² or higher. AMG 176 will be infused over 2 hours (± 5 minutes). Clinical visits on dosing days can be scheduled ± 1 day; however, safety and PK evaluations must occur at indicated time points, including a return to clinic 24 hours after dosing for safety and PK evaluations.
- ^g Azacitidine dosing: refer to the prescribing information for full details. The standard dose and schedule for azacitidine is as follows: Azacitidine will be administered at a dose of 75 mg/m² IV or SC daily on days 1 to 7 of each 4-week cycle.
- h Safety Labs: Safety labs include chemistry, hematology, urinalysis, and coagulation analytes. See Protocol for the list of analytes (Table 11-1). Pre-dose safety labs are to be collected per the SOA and can be collected up to approximately 24 hours before treatment begins unless otherwise indicated (eg, TLS monitoring test).
 - CBC with differential (differential not required if WBC \leq 0.5 k/ μ L), at least once weekly for the 1st cycle, then every 2 to 4 weeks during cycles 2 to 6, and then every 4 weeks (\pm 14 days) thereafter as long as they are on study.
 - Serum chemistry profile at least once weekly for the 1st cycle, then every 2 to 4 weeks during cycles 2 to 6, and then at least every 4 weeks (± 14 days) during active treatment.

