- ⁱ TLS monitoring test: TLS monitoring tests consists of the chemistry analytes serum potassium, phosphorous, calcium, uric acid, and creatinine and will be performed at the timepoints in the SOA. The pre-dose samples must be collected within 4 hours before AMG 176 administration to ensure electrolytes are within normal range.

 Note: The pre-dose safety chemistry and TLS monitoring tests can be drawn at the same time provided they are collected within 4 hours before AMG 176 administration.
- ^j Cardiac monitoring tests: Cardiac monitoring tests include the following analytes: troponin (I or T), creatine kinase-muscle/brain (CK-MB), and N-terminal prohormone of brain natriuretic peptide (NT-pro-BNP). These cardiac monitoring tests will be collected at the time points specified in the SOA and analyzed locally. In addition, samples will need to be submitted to the central lab. Refer to the central lab manual.
- k Pregnancy test (serum or urine). Applies to females of childbearing potential and will be performed locally at screening, prior to each treatment cycle (pre-dose), end of treatment, and at the safety follow-up visit. Additional on-treatment pregnancy testing may be performed at the investigator's discretion if there is suspicion that a female subject is pregnant or per local laws and regulations.
- ¹ HIV: to be performed only if required by local regulatory authorities.
- ^m PK: PK samples should be collected at the exact nominal time point as noted. For pre-dose PK sample, the sample should be collected within 1 hour before the dose. For all other timepoints, PK samples should be collected within ± 15 min of the designated time points. If unable to collect a PK sample at the specified nominal time point, then collect the sample as close as possible and record the actual collection time. Note: It is important to document the exact date and time of investigational product administration and PK sample collection.
- ⁿ AMG 176 PK: samples collected and analyzed for AMG 176 at the timepoints indicated. All AMG 176 timepoints are relative to start of infusion.
- o Azacitidine PK: samples collected and analyzed for azacitidine at the timepoints indicated. All azacitidine timepoints are relative to azacitidine administration.

Protocol Number: 20200392

Date: 28 April 2022 Page 27 of 149

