- Monitoring of electrolyte values is required prior to dosing anytime a dose is higher than one previously given to the subject. This will include at the following times:
 - Prior to the week 1, day 1 dose.
 - Prior to each dose during the lead-in period.
 - Prior to the initial dosing at the target dose level.
- Prior to administering these doses, all electrolyte values (including LDH, potassium, uric acid, phosphorus, calcium, and creatinine) must be reviewed and within normal range (samples must be drawn within 24 hours prior to dosing of AMG 176). The investigator's decision to proceed with AMG 176 treatment initiation will be based on these laboratory values.

Within the first 24 hours after either the first dose or dose escalation, if any laboratory criteria for TLS are met, no additional AMG 176 doses should be administered until resolution. A rapidly rising serum potassium is a medical emergency.

Prophylactic dose reductions for potassium, phosphorus and/or uric acid values at the high end of normal range should be considered.

If the potassium, uric acid, inorganic phosphate and/or creatinine values are higher than the normal range or the calcium is lower or higher than the normal range, this (these) value(s) can be approved following a discussion between the Amgen Medical Monitor and investigator.

On the AMG 176 dosing days chemistry labs must be performed pre-dose (within 4 hours before AMG 176 administration), 2, 4, 8, 12, and 24 hours after the start of AMG 176 infusion. Pre-dose labs will be used as baseline to assess potential electrolytes abnormalities occurring post AMG 176 administration. These labs must be reviewed in real time by the investigator.

All 24-hour laboratory assessments may be taken \pm 2 hours, if necessary.

Monitor for signs and symptoms of TLS (eg, fever, chills, tachycardia, nausea, vomiting, diarrhea, diaphoresis, hypotension, muscle aches, weakness, paresthesias, mental status changes, confusion, and seizures). If any clinical features are observed, recheck potassium, phosphorus, uric acid, calcium, and creatinine within 1 hour.

Additional information on the management recommendations of laboratory abnormalities can be found in Section 11.2.

 Nephrology (or acute dialysis service) consultation should be considered on admission (based on investigator discretion) for hospitalized subjects per

Protocol Number: 20200392

Date: 28 April 2022 Page 56 of 149

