| 50 to 75 | 100 | 50 | 33 | |
| > 75 | 75 | 50 | 33 | |

WBC = white blood cell

If a nadir as defined in the table above has occurred, the next course of treatment should be given 28 days after the start of the preceding course, provided that both the WBC and the platelet counts are > 25% above the nadir and rising. If a > 25% increase above the nadir is not seen by day 28, counts should be reassessed every 7 days. If a 25% increase is not seen by day 42, then the subject should be treated with 50% of the scheduled dose.

Following dose modifications, a new cycle will be started and duration should return to 28 days.

Dose adjustment based on renal function and serum electrolytes:

- Unexplained reduction of sodium bicarbonate to < 20 mEq/L reduce dose by 50% on the next cycle
- Unexplained elevation of Blood Urea Nitrogen (BUN) or serum creatinine ≥ 2-fold above baseline - delay next cycle until values return to normal or baseline and dose reduce by 50% in the next treatment cycle.

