11.2 Appendix 2. Clinical Laboratory Tests

The tests detailed in Table 11-1 will be performed by the central laboratory and/or by the local laboratory. Additional analyte test results may be reported by the local or central laboratory, in accordance with standard laboratory procedures (eg, components of a hematology panel). All locally obtained test results are to be recorded in the eCRF. Pharmacokinetic,

Protocol-specific requirements for inclusion or exclusion of subjects are detailed in Sections 5.1 to 5.2 of the protocol.

Blood samples will be obtained by venipuncture before study drug administration. All laboratory tests must be reviewed by the investigator or qualified designee. Additional safety laboratory assessments may be performed if clinically indicated at the discretion of the investigator. The following tests listed in Table 11-1 will be conducted on samples collected by standard laboratory procedures.

Additional tests may be performed at any time during the study as determined necessary by the investigator or required by local regulations.

Protocol Number: 20200392

Date: 28 April 2022 Page 100 of 149

Table 11-1. Analyte Listing

Central Laboratory

PΚ

Bone marrow aspirate

Bone marrow biopsy

Cardiac enzymes including troponin-I, CK-MB, and NT-pro-BNP

| Local Laboratory | | | | |
|--|---|---|--|--|
| Chemistry | Hematology | Urinalysis | | |
| Albumin ALP | ANC ^a Hematocrit | Specific gravity pH | | |
| ALT AST Bicarbonate (optional) NT-pro-BNP (or BNP if NT-pro-BNP not available) BUN or Urea Calcium Chloride CK-MB Creatinine | Hemoglobina MCH MCHC MCV Plateletsa RBCs WBCs Differential: Neutrophils Lymphocytes | Blood Protein Ketones Bilirubin Glucose Leucocytes esterase (WBC) Microscopic exam (only needed for positive dipstick and should include the following): Epithelial Bacteria | | |
| Direct bilirubin GGT Glucose LDH Magnesium | Monocytes Eosinophils Basophils Blasts^a | CastsCrystalRBCsWBCs | | |
| Phosphorus | Coagulation | Other Labs | | |
| Potassium Sodium Total bilirubin Total protein Troponin (I or T) Uric acid Haptoglobin | PT or INR aPTT | Pregnancy HBsAg HBsAb HBcAb Hepatitis C antibody HCV PCR (if applicable) HBV PCR (if applicable) | | |

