ALP = alkaline phosphatase; ALT = alanine aminotransferase; ANC = absolute neutrophil count; aPTT = activated partial thromboplastin time; AST = aspartate aminotransferase; BNP = B type natriuretic protein; BUN = blood urea nitrogen; CK-MB = creatinine kinase muscle/brain; DILI = drug induced liver injury; GGT = gamma-glutamyl transferase; HBcAb = hepatitis B core antibody; HBsAb = hepatitis B surface antibody; HBsAg = hepatitis B surface antigen; HBV = hepatitis B virus; HCV = hepatitis C virus; INR = international normalized ratio; LDH = lactate dehydrogenase; MCH = mean cell hemoglobin; MCHC = mean cell hemoglobin concentration; MCV = mean cell volume; NT-pro-BNP = N-terminal prohormone of brain natriuretic peptide; PCR = polymerase chain reaction; PK = pharmacokinetics; PT = prothrombin time; PTT = partial thromboplastin time; RBC = red blood cell; WBC = white blood cell.

^a Peripheral blood counts for MDS disease assessments will include ANC, platelets, hemoglobin, and blasts.

If the subject is being followed for possible DILI, the following analytes may be tested at the local laboratory depending on the clinical situation (see Section 11.7):

Protocol Number: 20200392

Date: 28 April 2022 Page 101 of 149

Table 11-2. DILI Potential Analyte Listing

| Chemistry | Total bilirubin, direct bilirubin, ALP, LDH, AST (SGOT), ALT (SGPT), creatine kinase, ferritin, gamma-glutamyl transferase, haptoglobin | |
|-------------|---|--|
| Hematology | Hemoglobin, Platelets, RBC Morphology, WBC Count, WBC Differential | |
| Coagulation | PT, INR | |

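### The azacitidine halving rule for a low bicarbonate relies on a test that the protocol's laboratory list marks as optional

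*Protocol*

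**What the plan says.** Protocol Section 6.2.2.3 gives two azacitidine dose rules under renal function and serum electrolytes. The first reads "Unexplained reduction of sodium bicarbonate to < 20 mEq/L reduce dose by 50% on the next cycle". The second delays the next cycle and then halves the dose when BUN or serum creatinine rises, unexplained, to at least twice baseline.

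The tests a site must run are set elsewhere. Footnote h of the Schedule of Activities (Section 1.3) defines the safety laboratories by pointing to Table 11-1, and Section 8.4.3 defines the protocol-required assessments by pointing to Section 11.2, which contains that table. In its local chemistry column the entry is "Bicarbonate (optional" (closing bracket not shown). Footnote h sets the sampling frequency without naming analytes: "Serum chemistry profile at least once weekly for the 1st cycle, then every 2 to 4 weeks during cycles 2 to 6".

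**The concern.** The dose rule is an instruction, but the list a site works from lets it skip the only measurement that can trigger that instruction. A subject whose bicarbonate is never measured never meets the rule, and the site has still followed the laboratory list. What is at stake is a stated safety measure for azacitidine recipients: a next-cycle reduction that the protocol intends might not be made because the value was never obtained.

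**Working it through.** No arithmetic beyond a count is needed. The check is whether any part of the two documents makes bicarbonate a required test.

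1. **The analyte list itself.** The local chemistry column of Table 11-1 has 24 analytes. Bicarbonate is the only one marked optional. BUN (or urea) and creatinine carry no such mark. Of the three laboratory triggers in the renal and electrolyte block (bicarbonate, BUN, creatinine), one is optional and two are not.

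2. **General statements about Table 11-1.** Section 11.2 says that the tests in the table will be performed. That sentence takes the table as written, including its optional mark, so it does not turn an optional test into a required one. Footnote h and Section 8.4.3 lead back to the same table.

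3. **Tumor lysis panel.** Footnote i of the Schedule of Activities states "TLS monitoring tests consists of the chemistry analytes serum potassium, phosphorous, calcium, uric acid, and creatinine". Sections 8.4.3.2 and 11.9.2 give the same five analytes. Bicarbonate is not among them.

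4. **Pre-dose electrolyte review.** Section 6.1.4.1 requires that "all electrolyte values (including LDH, potassium, uric acid, phosphorus, calcium, and creatinine) must be reviewed and within normal range", and Section 11.9.3 repeats this. Bicarbonate is not named. The requirement is tied to first, lead-in, ramp-up and first target doses, and is not a check in every cycle.

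5. **Liver injury work-up.** Table 11-2 is introduced with "the following analytes may be tested at the local laboratory depending on the clinical situation". It is conditional, and it does not list bicarbonate.

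6. **Other mentions.** Table 11-6 refers to sodium bicarbonate as a treatment for hyperkalemia and warns against combining it with rasburicase. It does not ask for a measurement.

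7. **Discretionary testing.** Section 11.2 adds "Additional safety laboratory assessments may be performed if clinically indicated at the discretion of the investigator". This permits the test but does not require it.

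8. **SAP.** It describes listings and analyses and adds no laboratory test.

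Bicarbonate is thus named once as an analyte, marked optional, and once as a dose trigger. Nothing in the two documents connects the two entries.

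**The case against.** The strongest reply has three parts.

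First, the protocol leans on documents that are not available here. Footnote g and Sections 2.2.3.2, 6.1.2 and 6.2.2.3 refer to the azacitidine prescribing information, and Section 8.4.3 refers to a laboratory manual. Either might require bicarbonate. This stands as a limit: the finding is that no requirement appears in the protocol or SAP, not that none exists.

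Second, the wording in Section 6.1.4.1 is open, because a list introduced by *including* need not be complete, and Section 6.2.2.3 itself groups bicarbonate with electrolytes. One could argue that bicarbonate is covered before the first doses. That reading is weak against an explicit optional mark, and it would still not supply a value in later cycles.

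Third, the consequence is small. Investigators may order extra tests, Section 6.2.2 allows dose reductions on clinical judgement, and BUN and creatinine monitoring is not optional. All of this stands and sets the severity. It does not remove the mismatch: discretion is no substitute for the input to a stated rule, and BUN and creatinine show only the toxicity that moves those markers.

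A reader might also infer that the rule fails for lack of a baseline value. The documents do not support that. The trigger is an absolute threshold and does not mention baseline, whereas the neighbouring BUN and creatinine rule does. Any earlier value would show a fall.

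**Conclusion.** The mismatch is real and minor. Section 6.2.2.3 depends on a test that Table 11-1 leaves optional, so a site can follow the laboratory list and be unable to apply the dose rule. Marking it optional is reasonable for Part 1A, where no azacitidine is given. What is missing is a qualifier for azacitidine recipients.

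Two stronger readings are tempting and should not be drawn.

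- *That dose reductions were missed, or that reported results are affected.* The documents give neither the number of azacitidine recipients nor the frequency of an unexplained fall. The SAP states that Part 2 did not enroll (Section 3.1) and that the study was terminated early (Section 7.1). It plans a response listing for Part 1A only (Section 9.5.2), marks exposure to non-investigational product as not applicable (Section 9.6.9), and names only AMG 176 for pharmacokinetic parameters (Section 9.7). This suggests few or no azacitidine-treated subjects but does not prove it.
- *That the number of missing values or the longest unmonitored gap can be computed.* Section 6.1.2 allows a course every 4 to 8 weeks, with longer delays possible, and Section 4.1.2 lets treatment continue until progression or another stopping criterion. Any such figure would rest on an assumed cycle length and number of cycles.

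The conclusion assumes that neither the prescribing information nor the laboratory manual requires the test. If either does, the remedy is only to bring Table 11-1 into line.

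**What to change.** In Table 11-1, make bicarbonate required for subjects receiving azacitidine (Part 1B and Part 2) in each scheduled safety chemistry sample, including the pre-dose day 1 sample of each cycle. Leave it optional for Part 1A. The 20 mEq/L threshold and the 50% reduction stay as they are.

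The samples are already planned. Footnote h states "Pre-dose safety labs are to be collected per the SOA and can be collected up to approximately 24 hours before treatment begins", so no extra visit or blood draw is needed. The downside is one more analyte to report from each sample. The change is one qualifier, made by protocol amendment with IRB/IEC submission (Section 11.3). If azacitidine dosing in this study has ended, an amendment would bring little, and the correction matters mainly for any later use of this protocol text.

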6.2.3 Hepatotoxicity Stopping and Rechallenge Rules

Refer to Section 11.7 for details regarding DILI guidelines, as specified in the Guidance for Industry Drug-Induced Liver Injury: Premarketing Clinical Evaluation, July 2009.

6.3 Preparation/Handling/Storage/Accountability

Guidance and information on drug accountability for the investigational product and/or other protocol-required therapies and/or devices will be provided to the site.

6.4 Measures to Minimize Bias: Randomization and Blinding

6.4.1 Method of Treatment Assignment

Subjects who meet eligibility criteria will be assigned to treatment with AMG 176.

The treatment assignment date is to be documented in the subject's medical record and on the enrollment CRF.

An Amgen representative will notify the site in writing when a cohort is open to screen and enroll subjects. The notification will include the cohort number and dose level in

Protocol Number: 20200392

Date: 28 April 2022 Page 71 of 149

which subjects will be enrolled. Enrollment of subjects in Part 1A and Part 1B will be based on availability in the cohort and agreement between the investigator and Amgen Medical Monitor.

6.4.2 Blinding

This is an open-label study; blinding procedures are not applicable.

6.5 Treatment Compliance

When subjects are dosed at the site, they will receive AMG 176 and azacitidine directly from the investigator or designee, under medical supervision. The date and time of each dose administered in the clinic will be recorded in the source documents and recorded in the CRF.

6.6 Treatment of Overdose

Higher doses of AMG 176 may be associated with cardiac troponin elevation. For management of troponin and other cardiac enzyme elevation, please refer to Sections 6.2.2.1 and 6.2.2.2.5.

Refer to the approved product label for azacitidine for information related to azacitidine overdose.

6.7 Prior and Concomitant Treatment

6.7.1 Prior Treatment

Prior therapies that were being taken from 2 years prior to enrollment through the informed consent should be collected. For prior therapies being taken for the disease under study (eg, steroids, chemotherapy on oncology studies), collect therapy name, indication, dose, unit, frequency, start date, and stop date. For all other prior therapies, collect therapy name, indication, dose, unit, frequency, route, start date, and stop date.

6.7.2 Concomitant Treatment

Throughout the study, investigators may prescribe any concomitant medications or treatments deemed necessary to provide adequate supportive care except for those listed in Section 6.1.7.

Concomitant therapies are to be collected from informed consent through the 30 days (+ 3 days) after the last dose of protocol-required therapies. For concomitant therapies being taken for the disease under study (eg, steroids, chemotherapy on oncology studies), assist in the evaluation of efficacy or safety endpoints, in a specific class, collect therapy name, indication, dose, unit, frequency, start date, and stop date.

Protocol Number: 20200392

Date: 28 April 2022 Page 72 of 149

For all other concomitant therapies, collect therapy name, indication, dose, unit, frequency, route, start date, and stop date.

The investigator must be informed as soon as possible about any medication taken from the time of screening until the end of the clinical phase of the study (final study visit). Any concomitant medication(s), including herbal preparations, taken during the study will be recorded in the electronic Case Report Form (eCRF). The minimum requirement is that drug name, dose, and the dates of administration are to be recorded. Additionally, a complete list of all prior cancer therapies will be recorded in the eCRF.

Subjects should receive full supportive care during the study, including transfusions of blood and blood products, and treatment with antibiotics, anti-emetics, anti-diarrheals, and analgesics, G-CSF and other care as deemed appropriate, and in accordance with their institutional guidelines. Hydroxyurea may be administered according to standard practice prior to the first cycle of AMG 176 treatment for subjects with high WBC (> 15000 cells/uL) and during the first cycle but not on days of AMG 176 administration.

6.7.2.1 Antifungal Prophylaxis

Use of micafungin and amphotericin B for antifungal prophylaxis is allowed for neutropenic subjects.

